## 457   **2.4 Examination Procedures**

### 458   **2.4.1 Historical Information**

459   Historical information to be collected will include: date of birth, gender, race, ethnicity, prior  
460   amblyopia therapy (e.g., glasses, patching, pharmacologic, filters, vision therapy), refractive  
461   correction, and history of allergy/intolerance to bandage adhesive.

462 **2.4.2 Clinical Testing for Enrollment**

- 463 1. Visual acuity in each eye (right eye first) is measured by the ATS single-surround eETDRS  
464 testing protocol on the Electronic Visual Acuity Tester. The protocol for conducting the  
465 visual acuity testing is described in the ATS Testing Procedures Manual. Aspects of the  
466 testing protocol that are specific to this study are indicated below:
- 467 • Testing must be done without cycloplegia (with spectacles, if worn) no more than 7 days  
468 prior to randomization.
  - 469 • Because the patient needs to be wearing spectacles that provide best visual acuity to be  
470 enrolled, trial frames/phoropter with a different correction cannot be used to measure  
471 acuity at enrollment.
  - 472 • If the patient has difficulty with the acuity testing, often he or she will perform better  
473 when the testing is repeated. At the investigator's discretion, acuity can be retested on  
474 the same or a subsequent day to assess eligibility.
- 475 2. Ocular motility examination
- 476 • Measurement of predominant alignment by Simultaneous Prism and Cover Test (SPCT)  
477 in primary position at distance and near.
  - 478 • Testing must be done without cycloplegia (with spectacles if worn) no more than 7 days  
479 prior to randomization
- 480 3. Ocular examination as per investigator's clinical routine to rule out a cause for reduced visual  
481 acuity other than amblyopia
- 482 ➤ if performed within prior 6 months, does not need to be repeated at time of  
483 enrollment.
- 484 4. Binocularity testing (without cycloplegia): Titmus Fly and Randot Preschool Stereoacuity  
485 test
- 486 5. Cycloplegic refraction using cyclopentolate 1% as per investigator's usual routine
- 487 ➤ if performed within prior 6 months, do not need to repeat at time of enrollment

488 **2.5 Randomization of Eligible Patients**

489  
490 Assuming that visual acuity in the amblyopic eye on the better of the initial or repeat tests is  
491 20/40 to 20/100, inclusive, and acuity in the sound eye is 20/25 or better, the patient will be  

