**529 3.1.1 Measurement of Visual Acuity**

530 Prior to each in-office therapy session the vision therapist (or other ATS certified visual acuity  
531 tester) will measure the visual acuity of each eye using the eETDRS protocol (*the protocol for*  
532 *conducting the visual acuity testing is described in the ATS Testing Procedures Manual*). The  
533 person completing the visual acuity measurement for in-office therapy sessions will not be  
534 required to be masked to the patient's treatment assignment.

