#### 574 **3.1.7 Initial In-Office Therapy Visit**

575 The initial in-office therapy visit must be scheduled within 10 days of randomization.

576 Scheduling on the day of randomization is permitted.

577  
578 Study treatment commences on the day of the first in-office vision therapy session. At the end of  
579 the session, patches and the at-home vision therapy software should be given to the patient. The  
580 patient and parent are instructed in their use and given a copy of the treatment instruction sheet.  
581 They are also given a calendar on which to record the amount of time spent patching and using  
582 the home VT software each day.

583  
584 Patients in the active group should be instructed to patch 1 hour that day. No near activities or  
585 home VT are completed that day. This is the same as other days on which an in-office therapy  
586 visit is completed.

587  
588 Patients in the control group should be instructed to patch 2 hours that day and perform 1 hour of  
589 near activities while patched. No (control) home VT is completed that day. This is the same as  
590 other days on which an in-office visit is completed.

591  
592 Both treatment groups are instructed to patch 2 hours and perform 1 hour of near activities of  
593 which ½ hour should be spent using the at-home VT software (either active or control software)  
594 starting the day after the 1st in-office treatment visit.

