## 644 **3.3 Home Calendar Logs**

645

646 Parents will record the amount of time the patient wore the patch at home each day.  
647  
648 The calendars will be brought to the weekly office visits and a summary of the data will be  
649 entered onto the study website, along with other data collected at therapy visits.  
650  
651 At each visit, the logs will be reviewed by the therapist and an assessment of patching  
652 compliance recorded on the Follow-up Examination Form.  
653

655 **4.1 Follow-up Schedule**

656

657 All patients will have the following study visits:

- 658 • Weekly office visits  $\pm$  4 days for 16 weeks for administration of in-office vision therapy
- 659 • 17-week masked outcome visit  $\pm$  1 week

660 **4.2 Testing Procedures**661 **4.2.1 Weekly In-Office Vision Therapy Visits**662 The following activities/testing will be performed at the weekly office visits in the specified  
663 order:

- 664 • Binocular diplopia query
  - 665 ○ If a patient reports the onset of constant diplopia, treatment will be discontinued. If
  - 666 diplopia has resolved at the next week's office visit, therapy will be reinstated;
  - 667 however, anti-suppression therapy will not be performed for those assigned to
  - 668 Active vision therapy
- 669 • Measurement of visual acuity in each eye by the eETDRS testing protocol on the  
670 Electronic Visual Acuity Tester
  - 671 ○ The right eye is tested first, then the left eye
  - 672 ○ Testing is performed without cycloplegia with spectacles (if worn)
- 673 • In-Office Vision Therapy
  - 674 ○ Active or Control vision therapy based on randomization
- 675 • Completion of the therapy progress checklist

676

677 All patients will continue to have weekly in-office treatment sessions even if the visual acuity  
678 reaches 20/20 during the study.

679

680 All procedures at weekly vision therapy visits are permitted to be performed by a person who is  
681 unmasked to the patient's treatment assignment.682 **4.2.2 Scheduling of Weekly In-Office Vision Therapy Visits**

683 Ideally, treatment visits should be exactly 7 days apart; however, this will not always be possible.  
684 As such, we have established acceptable visit windows for the time between each in-office vision  
685 therapy visit. The acceptable window for each appointment is  $\pm$  4 days from the original  
686 targeted date (as calculated from the initial therapy session). Furthermore, no more than two  

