## 993 **8.2 Primary Outcome Analysis**

994

995 The primary analysis will consist of a comparison of proportions of patients in the two treatment  
996 groups who have 20/25 or better visual acuity at the 17-week outcome exam, with adjustment for  
997 baseline visual acuity, using logistic regression. The primary analysis will follow the ‘intent-to-  
998 treat’ principle in which patients are analyzed according to randomized treatment assignment,  
999 regardless of whether the treatment was actually received or completed. Dropouts will be  
1000 counted as treatment failures in the primary analysis.

1001

1002 A secondary analysis that counts study dropouts as treatment successes will be performed. The  
1003 true treatment effect must be bracketed within the estimated treatment difference obtained in the  
1004 primary analysis and this secondary analysis. If these are within 10% of each other using the  
1005 absolute difference, the primary analysis will be considered the definitive analysis. Otherwise,  
1006 both estimates will be included in the publication of study results along with a discussion of the  
1007 implications for study conclusions and patient management.

1008

1009 A secondary analysis that estimates the treatment difference based on study completers only also  
1010 will be performed.

1011

1012 The treatment effect in subgroups based on baseline factors will be assessed in preplanned  
1013 secondary analyses of the primary outcome. The subgroups of interest will be those based on  
1014 baseline amblyopic eye visual acuity, age, baseline stereoacuity, prior treatment, practice type  
1015 (ophthalmology or optometry), and treatment compliance (excellent/good or fair/poor). In  
1016 accordance with NIH guidelines, estimates of treatment effect by gender and race/ethnicity also  
1017 will be computed.

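### Section 8.2 lists treatment compliance as a baseline-factor subgroup, but it is rated after randomisation, so treatment comparisons within compliance strata are open to bias

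*Protocol*

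**What the plan says.** Protocol section 8.2 opens its subgroup paragraph with "The treatment effect in subgroups based on baseline factors will be assessed in preplanned" secondary analyses of the primary outcome. The list that follows names baseline amblyopic-eye acuity, age, baseline stereoacuity, prior treatment and practice type, and then "and treatment compliance (excellent/good or fair/poor". No caveat or separate method is attached to the last item.

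Section 3.3 describes how compliance is obtained. "Parents will record the amount of time the patient wore the patch at home each day", and then "At each visit, the logs will be reviewed by the therapist and an assessment of patching" compliance is entered on the Follow-up Examination Form. Under section 3.1.7 the calendar is handed out at the first in-office session, which is when treatment starts. That session may fall on the day of randomisation or up to 10 days later.

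On masking, section 4.2.1 states: "All procedures at weekly vision therapy visits are permitted to be performed by a person who is" unmasked to assignment. Section 3.1.1 has the therapist, or another certified tester, measure acuity before each session.

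The history items in section 2.4.1 ("Historical information to be collected will include: date of birth, gender, race, ethnicity, prior" amblyopia therapy, and so on) include no compliance measure.

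**The concern.** A subgroup defined by a variable fixed before randomisation contains two randomised groups, so the difference within it estimates a treatment effect. A subgroup defined by something that happens afterwards does not have this property. The children rated excellent/good on active therapy need not resemble those rated excellent/good on control, because the assigned programme, the child's progress and the rater can all influence who receives that rating.

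Three features of this protocol make this more than a formality. The rater delivers the assigned therapy and so knows the arm. The same person may know the interim acuity. The two regimens differ in content, burden and office-day patching at home, and section 1.3 (Feasibility Phase) itself singles out adherence to weekly visits in the control group as an open question.

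What is at stake is interpretation. A preplanned finding that active therapy works, or fails to work, in compliant children would carry weight with clinicians. Under the present label it would be read as a baseline subgroup result.

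**Working it through.** **Step 1: is compliance a baseline variable in this protocol?**

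| Question | Protocol | Answer |
|---|---|---|
| How is it labelled? | 8.2 | Among subgroups based on baseline factors |
| When do its data begin? | 3.1.7 | Calendar given at the first therapy session, after randomisation |
| When is it rated? | 3.3 | At visits during treatment |
| Who rates it? | 3.3, 4.2.1 | The therapist, who delivers the assigned therapy; masking is not required |
| Could the rater know interim acuity? | 3.1.1 | Yes, the therapist may measure it before the session |
| Is there a baseline measure? | 2.4.1 | None among the listed items |

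The label in 8.2 conflicts with 3.1.7 and 3.3.

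**Step 2: does it touch the plan's own figures?** Section 8.1 gives no figure for this subgroup. Its total of 222 (30% versus 50%, one-sided 5%, 90% power) reproduces. The continuity-corrected two-proportion formula gives 111 per arm, and exact one-sided Fisher power at 111 per arm is 0.9001. Compliance does not enter that calculation.

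**Step 3: how large could the spurious difference be?** The document gives no inputs for this, so those below are assumptions. In each scenario the treatment has no effect on anyone and overall success is 30% in both arms, the control rate in section 8.1.

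*Set 1.* Half the children have a good prognosis (45% success) and half a poor one (15%). If g and b are the proportions complying in the two halves, then

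success among compliers = (0.5·g·0.45 + 0.5·b·0.15) / (0.5·g + 0.5·b),

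and the non-complier formula uses 1−g and 1−b.

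| Scenario | Control g / b | Active g / b | Compliers, active − control | Non-compliers, active − control |
|---|---|---|---|---|
| a | 80% / 60% | 80% / 60% | 32.1% − 32.1% = 0 | 25.0% − 25.0% = 0 |
| b | 75% / 65% | 80% / 60% | 32.1% − 31.1% = +1.1 | 25.0% − 27.5% = −2.5 |
| c | 70% / 70% | 90% / 50% | 34.3% − 30.0% = +4.3 | 20.0% − 30.0% = −10.0 |
| d | 70% / 70% | 95% / 35% | 36.9% − 30.0% = +6.9 | 17.1% − 30.0% = −12.9 |

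For example, in scenario c the active compliers give (0.5·0.90·0.45 + 0.5·0.50·0.15)/0.70 = 0.24/0.70 = 34.3%. Differences are in percentage points, computed before rounding. Exchanging the arms reverses every sign.

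*Set 2.* 60% of children are motivated (40% success) and 40% less so (15%); 0.60·0.40 + 0.40·0.15 = 30%. In control only the motivated comply. In the active arm half of the less motivated comply as well.

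- Active compliers: (0.60·0.40 + 0.20·0.15)/0.80 = 0.27/0.80 = 33.75%.
- Control compliers: 40.0%.
- Difference: −6.25 points, with no true effect.

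**Step 4: how does this compare with sampling error?** In Set 2 there are about 111·0.80 ≈ 89 active and 111·0.60 ≈ 67 control compliers. The standard error of the difference is √(0.3375·0.6625/89 + 0.40·0.60/67) ≈ 0.078, or 7.8 points. The spurious −6.25 is less than one standard error.

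**The case against.** The strongest reply is that the design limits how far compliance can diverge by arm. What section 3.3 rates is patching, which is prescribed alike in both arms on non-office days (section 3.2). Office-day hours are adjusted to equalise patching time (section 3.2.1). Parents, who keep the logs, are masked, as are the children (section 1.3). A large arm-specific shift is therefore less likely than the extreme scenarios suggest, and in scenario a the spurious difference is exactly zero. Even the −6.25 points of Set 2 would not by itself make a convincing subgroup claim. This stands, and it is why the result cannot be called biased outright. It does not restore the protection of randomisation, because the rating is still made during treatment by someone who knows the arm.

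It can also be said that section 8.2 does not define treatment compliance, so identifying it with the patching rating in 3.3 is an inference. That is fair. However, 3.3 describes the only compliance rating in the protocol, and any measure of compliance with study treatment would also arise after randomisation. A related reading, that this subgroup would show the effect in children who adhere to vision therapy, is not supported: the rating described is of patching, which both arms receive.

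Finally, chapter 8 describes itself as a synopsis to be superseded by the final analysis plan, and the analysis is secondary. Both points limit the consequence. Neither cures the text, since 8.2 does not leave a detail open but places a post-randomisation variable under a baseline heading.

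**Conclusion.** The point holds as a misclassification with a limited consequence. Treatment comparisons within compliance strata are not protected by randomisation and are open to bias of unknown size and direction. Over the assumed null scenarios the spurious difference runs from 0 to about 6 to 7 points in either direction among compliers. Among non-compliers it runs from 0 to about 13 points, again in either direction. For scale, section 8.1 treats 20 points as the smallest worthwhile improvement. All these figures rest on assumed prognosis and compliance rates, and none is an estimate for this trial.

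A reader might infer that the compliance subgroup result is certain to be biased, or that the trial's main conclusion is at risk. The documents support neither. The bias is zero if compliance relates to prognosis in the same way in both arms. The primary analysis is intent-to-treat in all randomised patients, so it and N = 222 are unaffected.

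**What to change.** In section 8.2, remove treatment compliance from the list of baseline-factor subgroups and state that compliance will be reported descriptively by treatment group. If the final analysis plan repeats the list, make the same edit there.

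If a treatment effect by compliance category is still wanted, label it exploratory and based on a post-randomisation variable, and state its assumptions. A standard instrumental-variable complier analysis does not apply directly: it needs a measure of receipt of the randomised component, whereas patching is given in both arms. A principal-stratification analysis would be possible, but it rests on strong assumptions that would have to be written down.

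The cost is a short text change and the loss of one preplanned compliance subgroup result. No new data, visits or patients are needed.

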## 1018 **8.3 Safety Analysis**

1019

1020 Safety data consisting of the number and proportion of patients in each treatment group  
1021 experiencing the following events will be compiled and included in all reports to the DSMC:

- 1022       • Loss of 2 or more lines in sound eye visual acuity from baseline to the 17-week masked  
1023       exam  
1024       • Development of diplopia at any time during treatment and whether it has resolved by the  
1025       17-week masked exam  
1026       • Development of a new ocular deviation and whether it has resolved by the 17-week  
1027       masked exam

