### 260 Primary Analysis

261 The primary outcome measure is the proportion of patients with visual acuity of 20/25 or better

262 in the amblyopic eye at the 17-week masked exam. These patients will be considered treatment

263 responders. The primary analysis will consist of a comparison between the 2 treatment groups of

264 the proportion of treatment responders with adjustment for baseline visual acuity.

265

266 Secondary outcomes are stereoacuity at the 17-week masked exam, mean improvement in visual

267 acuity at the 17-week masked exam, and rate of improvement of visual acuity.

268

269 Sound eye visual acuity will be reported for each treatment group at the 17-week masked exam

270 as mean change from baseline, distribution of number of lines of change from baseline, and

271 number and proportion of patients losing 2 or more lines from baseline.

272

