**847 7.2.1 Risk of Patching**

848 In view of the small number of hours of daily patching, significant skin irritation is unlikely. If  
849 irritation occurs, the parent will be advised to put an emollient on the skin and discontinue use of  
850 the patch for a day.

851 ➤ If a skin reaction to the patch occurs, or an allergic reaction occurs serious enough to  
852 discontinue patching, the investigator should call his or her assigned Steering Committee  
853 member to discuss the case. An alternative adhesive patch may be tried. If patching with  
854 adhesive patches is discontinued, then the patient should be tried with a felt “Patch  
855 Works” type patch placed on the lens of the glasses over the non-amblyopic eye (or on  
856 plano lens if patient not wearing spectacles).

857

858 Patching potentially could decrease the visual acuity in the sound eye, although this is almost  
859 always reversible. This occurrence is extremely unlikely in view of the age of the patient and the  
860 small number of hours of daily patching. The diagnosis and management of reverse amblyopia  
861 is left to the investigator’s judgment.

862

863 Patching could precipitate the development of a manifest ocular deviation. If treatment  
864 precipitates the development of a strabismus (e.g., esotropia in child with hyperopia), the parent  
865 will be advised to have the patient see the investigator as soon as possible. The decision to  
866 continue or discontinue therapy will be left to the discretion of the investigator and parent. If the  
867 decision is made to continue treatment, the patient will remain in their assigned group.

868

869 There are some activities that should not be performed when patched due to the level of vision in  
870 the amblyopic eye and some reduction in visual field. These activities include riding a bike, in-  
871 line skating, skateboarding, or other activities in which the child could get hurt. The consent  
872 form will explicitly instruct parents not to allow their child to perform such activities while  
873 patched.

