#### 1028   **8.4 Interim Analysis**

1029  
1030   An analysis of primary outcome data, secondary outcome data, and safety data will be provided  
1031   to the DSMC twice each year. A formal statistical plan for interim monitoring of primary  
1032   outcome data will be developed in conjunction with the DSMC.

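### Section 8.3 counts sound-eye loss only at the 17-week exam, so losses that recover, precede dropout or occur in a child still on treatment are missing from the DSMC row

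*Protocol*

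**What the plan says.** Section 8.3 lists three safety events and says that patients "experiencing the following events will be compiled and included in all reports to the DSMC". They are:

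- "Loss of 2 or more lines in sound eye visual acuity from baseline to the 17-week masked" exam;
- "Development of diplopia at any time during treatment and whether it has resolved by the" 17-week masked exam;
- "Development of a new ocular deviation and whether it has resolved by the 17-week" masked exam.

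The synopsis (section 1.3, Primary Analysis) uses the same single time point for the sound eye: "Sound eye visual acuity will be reported for each treatment group at the 17-week masked exam". Section 8.4 sends safety data "to the DSMC twice each year".

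Section 7.2.1 states the risk: "Patching potentially could decrease the visual acuity in the sound eye, although this is almost" always reversible. It then calls the event extremely unlikely and leaves diagnosis and management of reverse amblyopia to the investigator. The procedures for every weekly visit (section 4.2.1) include "Measurement of visual acuity in each eye by the eETDRS testing protocol on the" electronic tester. Under section 3.3, data from therapy visits are entered on the study website.

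**The concern.** Two of the three events are counted by onset, with a second classification for resolution. The third is a comparison of two time points. Nothing in the protocol explains the difference. Acuity is also the one objective measure taken every week: ocular alignment is not on the weekly list in section 4.2.1.

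What is at stake is the DSMC's view of a harm to the healthy eye of a child. A 2-line loss seen during treatment would not reach the row if the eye recovered by week 17, or if the child left before the exam. If the child is still on treatment at a report, the loss is at best delayed. A diplopia case with the same history would be in the table each time.

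**Working it through.** **1. The three definitions side by side**

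| Event (section 8.3) | Counted when | Resolution shown | Can be counted before week 17 |
|---|---|---|---|
| Diplopia | any time during treatment | yes | yes |
| New ocular deviation | on development | yes | yes |
| Sound-eye loss of 2 or more lines | at the 17-week exam | no | no |

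**2. What the sound-eye row omits if followed as written**

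- *Loss that recovers.* Acuity down 2 lines at week 6 and back by week 17 is a non-event.
- *No 17-week exam.* Section 8.2 has a rule for dropouts in the primary outcome (counted as failures). Section 8.3 has none for this row, so a loss recorded before dropout has nowhere to go.
- *Still on treatment at a report.* A loss at week 6 can enter the row no earlier than week 17, that is 17 − 6 = 11 weeks later. Diplopia at week 6 can be shown at once.

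The second and third omissions need no assumption about recovery.

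**3. Can the share lost through recovery be computed?**

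The protocol gives no figure to reproduce. Section 7.2.4 speaks of recovery with cessation or reversal of treatment, and sections 3.1 and 3.2 prescribe patching through the 17-week exam. Among affected children who attend that exam, let s be the share whose patching is stopped or reversed early, and r the share of those who have recovered by week 17. If recovery needs cessation, share missed = s × r. Both inputs are assumptions.

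| s | r = 0.50 | r = 0.80 | r = 0.95 |
|---|---|---|---|
| 0 | 0% | 0% | 0% |
| 0.25 | 12.5% | 20% | 24% |
| 0.50 | 25% | 40% | 47.5% |
| 0.75 | 37.5% | 60% | 71% |
| 1.00 | 50% | 80% | 95% |

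The range is 0% to 95%, and nothing in the protocol narrows it.

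**4. Noise from counting at more visits**

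Section 2.3 equates 15 letters with 3 lines, so 2 lines are 10 letters. Assume no true change, independent normal test errors with SD σ letters, one baseline test and 17 later tests (16 weekly visits and the 17-week exam).

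For one exam, the chance of a 10-letter loss is Φ(−10 / (σ√2)):

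- σ = 3: Φ(−2.36) ≈ 0.9%
- σ = 4: Φ(−1.77) ≈ 3.8%

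The multi-visit figures come from simulating 200,000 children per σ.

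| Rule | σ = 3 | σ = 4 | Expected among 222 children |
|---|---|---|---|
| 17-week exam only | 0.9% | 3.8% | 2 to 8 |
| Any single visit | 8.8% | 26.5% | 20 to 59 |
| Two consecutive visits | 1.0% | 6.0% | 2 to 13 |

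The last column multiplies each percentage by 222 and assumes complete visits. The two-visit rule brings chance events close to the level of the existing row at σ = 3, and to about one and a half times that level at σ = 4 (6.0 / 3.8 ≈ 1.6). σ is not given in the protocol, and the result is sensitive to it: at σ = 5 the two-visit figure is 13.5%.

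**The case against.** The strongest reply is that a single masked measurement is a reasoned choice. Section 4.2.3 requires a masked examiner at week 17, whereas weekly acuity may be taken by an unmasked therapist (section 3.1.1). Diplopia is a reported symptom, while a 10-letter fall is a threshold on a noisy repeated test, so different counting rules can be justified. Both arms patch for deliberately similar times (section 3.2.1), so sound-eye loss from patching is not the main contrast between them. Chapter 8 also describes itself as a framework that the final analysis plan will supersede. These points stand as reasons to keep the masked week-17 row. They do not explain why earlier losses should be left out of a safety table, and section 8.3 states a definition rather than leaving it open.

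The protocol covers part of the gap elsewhere. Section 8.8 reviews all cases of reverse amblyopia with no week-17 limit, but only in the 45-patient feasibility phase and without a definition. Section 8.4 sends safety data to the DSMC without saying that the three items in section 8.3 are all it sees.

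A reader might infer from the reversibility statement that most sound-eye losses would be missed, or that this is the main harm of patching. The documents support neither. Reversible is not the same as recovered by week 17, and a loss under continued patching may well still be present at the exam. Missing more than half through recovery requires s × r above 0.5, for example more than 53% of affected children stopping early when 95% of those recover. Section 7.2.1 expects the event to be extremely unlikely, section 7.1 expects withdrawals to be very infrequent, and no passage ranks sound-eye loss above the other risks.

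**Conclusion.** The point holds as a gap in one safety definition. As written, the section 8.3 row and the matching synopsis text omit sound-eye losses that recover before week 17, precede dropout, or occur in a child still on treatment at a DSMC report. The two neighbouring events are not treated this way, and the weekly acuity data needed to close the gap are already collected.

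Its size is not known. The share lost through recovery could be anywhere from none to nearly all, depending on stopping and recovery rates that the protocol does not give. The absolute number should be small if the event is as rare as section 7.2.1 expects. The sample size of 222 and the primary analysis are unaffected. This is a cheap improvement to safety reporting, not an error that threatens the trial.

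**What to change.** Keep the masked week-17 row unchanged and add one row to section 8.3, for example:

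*Sound-eye acuity 10 or more letters (2 or more lines) below baseline at two consecutive visits, at any point in treatment; and whether this had resolved at the 17-week masked exam.*

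List separately any child whose last visit before dropout shows such a loss without confirmation. That is a single unconfirmed value, and the two-visit noise figures do not apply to it. The 10-letter, two-measurement form follows the protocol's own definition of recurrence (section 5.4), although that definition allows both measurements on one day.

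The cost is one table row and a short listing from data already entered. There are two drawbacks, and a footnote should state both. Weekly testers may be unmasked. Some chance events will also be listed: about 1% of children with a per-test SD of 3 letters and 6% with 4, both assumed values, against about 9% and 27% without confirmation. The change alters no treatment rule.
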